8.10 Interim analysis

Not Applicable.

8.11 Data Safety Monitoring Board

The DSMB will be responsible for reviewing accumulated safety and efficacy data at intervals throughout the study.

The DSMB is periodically reviewing all safety data and raise alerts in case of negative or dangerous findings. Members of the DSMB will be selected based on their expertise by the SARA managing Board.

During the COVID-19 outbreak, the DSMB is meeting at least every other week to review its recommendation based on update of guidance from the national health agencies and local status.

Version Final 2.0, Date: 04JUN2021

In particular, the DSMB will evaluate the results of a formal pre-planned interim futility analysis and sample size reassessment. The DSMB will recommend to the Sponsor whether to continue, modify or stop the clinical trial based on futility but also on safety issues or other considerations not related to efficacy or safety. In case the study continues and the original sample size is retained, the DSMB will not communicate to anyone whether this is due to unfavorable or favorable results.

CHANGES TO PLANNED ANALYSIS FROM STUDY PROTOCOL

- The text from the protocol ''and for whom any follow-up information is available'' is not included in the definition of the safety population, thus more closely aligned with the definition in CPMP/ICH/363/96.
- The protocol mentioned '' The study would stop for futility at the interim analysis if a gait speed difference below the threshold defined in the SAP is observed." The interim analysis (IA) will no longer include the possibility of stopping for futility as all patients will have been recruited before the IA occurs. The details of the IA will be contained in the IA SAP.
- 'Month 6' is updated to 'Month 6/Month 9' in SAP due to COVID-19 except for section '5 SAMPLE SIZE AND POWER'
- 'Additional sensitivity analyses may be added in the SAP during the blind-review meeting if the number of missing data is important (more than 10%).' is removed from SAP, and section '8.7.6.1 Sensitivity Analyses of Missing data by Using Bayesian Multiple Imputation (MI) Methods' is added due to COVID-19.
- Additional analysis for primary endpoint is planned. Last assessment on treatment will be derived and analyzed.

9

10 **REFERENCES**

- 1. ICH Topic E3: Structure and Content of Clinical Study Reports (CPMP/ICH/137/95adopted December 1995).
- ICH Topic E9: Statistical Principles for Clinical Trials (CPMP/ICH/363/96 adopted March 1998).

Statistical Analysis Plan Protocol Number: BIO101-CL03

Version Final 2.0, Date: 04JUN2021

Page 49 of 69

VAR chg; RUN;

Pearson Correlation Co-efficient and Scatter Plot

```
PROC CORR DATA = dataset;
VAR PF 10 biomarker 1;
ODS OUTPUT PearsonCorr = PE;
RUN;
Data _NULL_;
SET PE;
IF n = 1 THEN CALL SYMPUT ('pear', PUT (PF 10, BEST6.));
ELSE CALL SYMPUT ('pval', PUT (pbiomarker_1, PVALUE8.4));
RUN;
PROC SGPLOT DATA=dataset;
SCATTER x= biomarker 1 y=PF_10;
REG x= biomarker 1 y=PF 10;
INSET ("Pearson" = "&pear" "P-value" = "&pval") /
BORDERITLE="Correlation co-efficient" POSITION=topleft;
```

RUN;

Note: Repeat the same for the each treatment group and the correlation between each endpoint specified and specified biomarkers.

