8.7.1.5 Pearson Correlation co-efficient

In order to the strength and direction of the linear relationship between the two variables, a Pearson correlation co-efficient along with the p-value will be presented.

The SAS code used to implement this test is given in Appendix A.

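### The SAP's correlation code fills the scatter-plot inset from the diagonal of the correlation table, so the inset would print 1 and a missing p-value

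*SAP*

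**What the plan says.** SAP section 8.7.1.5 states that "a Pearson correlation co-efficient along with the p-value will be presented" for a pair of variables, and adds: "The SAS code used to implement this test is given in Appendix A". The code is in Appendix A under the heading for the Pearson coefficient and scatter plot.

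The code works in three steps:

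- PROC CORR is run with "VAR PF 10 biomarker 1", and the table is saved by "ODS OUTPUT PearsonCorr = PE".
- A DATA step reads that table. On the first row it executes "IF n = 1 THEN CALL SYMPUT ('pear', PUT (PF 10, BEST6"; on any other row it executes "ELSE CALL SYMPUT ('pval', PUT (pbiomarker_1, PVALUE8.4".
- PROC SGPLOT draws the scatter and regression line, and prints the two stored values with "INSET ('Pearson' = '&pear' 'P-value' = '&pval".

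A closing note sets the scope of reuse: "Note: Repeat the same for the each treatment group and the correlation between each endpoint specified and specified biomarkers".

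Some underscores were lost when the PDF was read. Below, `PF_10`, `biomarker_1` and the automatic row counter `_N_` are written with them restored.

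**The concern.** A saved PROC CORR table for two variables is a square matrix in long form. It has one row per variable, with the correlations and p-values across the columns. Only the off-diagonal cells hold the wanted r and p; the diagonal cells describe each variable against itself. The DATA step takes one value from each row, so whether it lands on or off the diagonal depends on the order of the VAR list. With the order printed in Appendix A it lands on the diagonal both times.

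At stake is the pair of numbers shown on each biomarker scatter plot. These are the two quantities that section 8.7.1.5 says will be presented, and the inset is the only place where this code puts them on the figure. Because the code is a template to be repeated, the slip would be copied into each plot made from it.

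**Working it through.** **Inputs.** From Appendix A: VAR order `PF_10`, then `biomarker_1`; `pear` is taken from column `PF_10` on row 1; `pval` is taken from column `Pbiomarker_1` on the remaining row. From section 8.7.1.5: the intended result is r and p for the pair. The plan states no figure to reproduce.

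**Layout of the saved table**, with r and p the sample correlation of the pair and its p-value:

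| Row | `PF_10` | `biomarker_1` | `PPF_10` | `Pbiomarker_1` |
|---|---|---|---|---|
| 1 (`PF_10`) | 1 | r | missing | p |
| 2 (`biomarker_1`) | r | 1 | p | missing |

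**Trace of the DATA step.**

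- Row 1: `pear` = column `PF_10` = 1. The wanted r is in column `biomarker_1` of the same row.
- Row 2: `pval` = column `Pbiomarker_1` = missing. The wanted p is in column `PPF_10` of the same row.

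Neither off-diagonal cell is read.

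**Numerical check.** The table and the DATA step were emulated in Python. The documents give no biomarker correlations, so five true values were assumed, with n = 77 (the per-arm number in SAP Figure 1):

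| Assumed true correlation | Sample r | Sample p | Inset r | Inset p |
|---|---|---|---|---|
| -0.6 | -0.6331 | 0 to six decimals | 1 | missing |
| -0.3 | -0.2626 | 0.021065 | 1 | missing |
| 0 | 0.0815 | 0.481164 | 1 | missing |
| 0.3 | 0.4116 | 0.0002 | 1 | missing |
| 0.6 | 0.5213 | 0.000001 | 1 | missing |

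The inset does not change while the sample r runs from -0.6331 to 0.5213.

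**Reversed order.** With VAR `biomarker_1`, then `PF_10`, row 1 becomes the biomarker row, so its `PF_10` column holds r. Row 2 becomes the PF-10 row, so its `Pbiomarker_1` column holds p. The unchanged DATA step then returned 0.5213 and 0.000001 in the last case, which are the right values. The DATA step therefore suits the opposite VAR order; the two pieces of code do not match each other.

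**Scope.** The SAP table of contents lists correlations of the M6/M9 primary and key secondary endpoints with plasma biomarkers. That is three endpoints (gait speed, PF-10, handgrip) in three arms: 3 × 3 = 9 insets per biomarker, if each combination has its own plot. The body of that section is not visible in the public text, so the number of biomarkers is unknown.

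**The case against.** Four things can fairly be said for the plan.

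- PROC CORR itself is specified correctly, so the right r and p exist in its output. SAP section 1 places the table and figure templates in a separate document, and a table taken straight from PROC CORR would be correct. This stands, and it confines the fault to the inset.
- The error shows itself. A correlation of 1 with no p-value, repeated beside visibly scattered points, should be caught when the first figures are checked. This also stands, and it makes a misled reader unlikely.
- Appendix A is a template with placeholder names that must be edited for each use. That is true, but renaming variables leaves the row and column logic in place. For another endpoint the printed 1 would be that endpoint's correlation with itself. Section 8.7.1.5 also names this code as the implementation, so it deserves to be right.
- The extracted text is damaged. The point does not rest on the damage: the mismatch remains once the underscores are restored.

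A reader might go further and take the printed `n` as an ordinary variable, so that the coefficient would never be filled at all. The documents do not support this. Underscores are missing elsewhere in the same block (`PF 10`, `biomarker 1`), and the sensible reading is the automatic row counter.

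**Conclusion.** The point holds as a low-impact coding error. With the VAR order in Appendix A, the DATA step reads the two diagonal cells, and the inset prints 1 and a missing p-value in every unedited copy of the template.

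A reader might infer that the relation between biomarkers and efficacy would be misreported throughout. The documents do not support that. Only the inset text is wrong; the PROC CORR results, the points and the fitted line are unaffected, and the format in which r and p will finally be reported is not visible. The correlations also lie outside the Hochberg family of section 8.7.1.6, so no primary or key secondary conclusion depends on them.

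The conclusion assumes that the lost underscores are restored and that PROC CORR leaves the diagonal p-value missing. The latter is standard behaviour but was not run in SAS here. The diagonal coefficient of 1 holds by definition. Whatever is stored in the diagonal p-value cell, it is not the p-value for the endpoint and biomarker pair.

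**What to change.** Any one of these changes to Appendix A is enough:

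1. On row 1 set `pear` from `biomarker_1` and `pval` from `Pbiomarker_1`, and drop the ELSE branch so that row 2 cannot overwrite the p-value.
2. Reverse the list to VAR `biomarker_1 PF_10` and leave the DATA step unchanged.
3. Use VAR `biomarker_1` with WITH `PF_10`. The saved table then has one row and no diagonal; set `pear` from `biomarker_1` and `pval` from `Pbiomarker_1` on that row.

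The third is the safest for a template, because it has no diagonal to hit when variable names are swapped. The cost is a line or two of code, with no change to data, design or any other analysis. Making the edit before database lock also avoids having to explain a departure from the SAP code in the study report.

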Appendix B - Short Physical Performance Battery (SPPB)

Summary performance score: Each of the three performance measured is assigned a score ranging from 0 to 4, with 4 indicating the highest level of performance and 0 the inability to complete the test. For the test of balance, participants are assigned a score of 1 if they can hold a side-by-side standing position for 10 seconds but are unable to hold a semi-tandem position for 10 seconds; a score of 2 is assigned if they can hold a semi-tandem position for 10 seconds; a full-tandem position for 3 seconds; a score of 3 is assigned if they can stand in a full-tandem position for 3 seconds; a score of 4 is assigned if they can stand in a full tandem position for 10 seconds.

Four categories are computed for walking speed and chair stands, according to cut-off points that are based on quartiles of the time to perform each task assessed in the EPESE. The time of the faster of two walks is scored as follows: > 8.7 sec = 1; 6.21 to 8.70 sec = 2; 4.82 to 6.20 sec = 3; < 4.82 sec = 4; a score of 0 is assigned to participants unable to perform the test. The time required to perform five chair stands is scored as follows: $\ge 16.70 \text{ sec} = 1$; 13.70 to 16.69 sec = 2; 11.20 to 13.69 sec = 3; $\le 11.19 = 4$. A score of 0 is assigned to participants unable to perform the task. A summary score ranging from 0 (worst performers) to 12 (best performers) is calculated by adding subscores from the walking speed, chair stands and balance tests.

Appendix C - SF-36v2 Coding and Scoring

All questions will be scored as per the raw data valued collected on the CRF with the following exceptions. Seven questions will have their coding inversed so that 5=1, 4=2, 3=3, 2=4 and 1=5. These questions are: 6, 9a, 9d, 9e, 9h, 11b and 11d.

The SF-36v2 scoring system relies on an assumption of linearity among the responses. However, for three of the 36 questions, it was found that the intervals were not evenly spaced among some of the qualitative responses so the values were recoded to preserve the linearity assumption. The questions affected are question 1 (General Health) and questions 7 and 8 (Bodily Pain).

Question 1 (General Health)

Q1	Q1	Q1
(verbatim responses)	(raw value)	(recoded)
Excellent	1	5.0
Very good	2	4.4
Good	3	3.4
Fair	4	2.0
Poor	5	1.0

Question 7 (Bodily Pain)

Q7	Q7	Q7
(verbatim responses)	(raw value)	(recoded)
None	1	6.0
Very mild	2	5.4
Mild	3	4.2
Moderate	4	3.1
Severe	5	2.2
Very severe	6	1.0

Question 8 will have its score inversed too, but also depends on the response given for question 7, in the following manner:

Q7 (raw value)	Q8 (verbatim responses)	Q8 (raw value)	Q8 (recoded)
1	Not at all	1	6
2, 3, 4, 5 or 6	Not at all	1	5
any	A little bit	2	4
any	Moderately	3	3
any	Quite a bit	4	2
any	Extremely	5	1

If question 7 is not answered then question 8 will have its score recoded to preserve linearity, in the following manner:

Q7	Q8	Q8	Q8
(raw value)	(verbatim responses)	(raw value)	(recoded)
missing	Not at all	1	6.0
missing	A little bit	2	4.75
missing	Moderately	3	3.5
missing	Quite a bit	4	2.25
missing	Extremely	5	1.0

If more that 50% of items for a sub-score then, for the purposes of calculating the subscale score, the sub-scale score is considered as missing. If less that 50% are missing then the missing items are replaced by the individual subjects mean score for the remaining items in the sub-scale. Imputed item scores are only used for calculating the sub-scale score.

This transformation converts the lowest and highest possible sub-scale scores to 0 and 100, respectively (0 represents worst possible health state and 100 represents best possible health state):

Standardised Score = $\frac{(\text{sub-scale score} - \text{Lowest Possible Sub-scale Score})}{\text{Possible Sub-scale Score Range}} \ge 100$

Statistical Analysis Plan Protocol Number: BIO101-CL03

The lowest sub-scale value and the range of sub-scales values for each subscale of SF-36 are as follows:

Description of item	Lowest possible score	Range of Sub-scale score
PF-10	10	20
Role limitations due to-physical problems	4	16
Bodily Pain	2	10
General Health perceptions	5	20
Vitality	4	16
Mental Health	5	20
Role-limitations due to emotional problems	3	12
Social Functioning	2	8

The following is an example of the SAS® code used to divide the 36 questions (recoded as necessary) into the 8 sub-classifications and to transform the values to a 0 - 100 scale.

data SF36;

```
tot_PF=sum(of Q3A Q3B Q3C Q3D Q3E Q3F Q3G Q3H Q3I Q3J);
tot_RP=sum(of Q4A Q4B Q4C Q4D);
tot_BP=sum(of Q7 Q8);
tot_GH=sum(of Q1 Q11A Q11B Q11C Q11D);
tot_VT=sum(of Q9A Q9E Q9G Q9I);
tot_SF=sum(of Q6 Q10);
tot_RE=sum(of Q5A Q5B Q5C);
tot_MH=sum(of Q9B Q9C Q9D Q9F Q9H);
sf36_PF=((tot_PF - 10)/(20))*100;
sf36_BP=((tot_PF - 4)/(16))*100;
sf36_GH=((tot_BP - 2)/(10))*100;
sf36_SF=((tot_GH - 5)/(20))*100;
sf36_SF=((tot_SF - 2)/(8))*100;
```

Version Final 2.0, Date: 04JUN2021

Page 54 of 69

```
sf36_RE=((tot_RE - 3)/(12))*100;
sf36_MH=((tot_MH - 5)/(20))*100;
label sf36_PF = "Physical functioning score (10 items)"
sf36_RP = "Role-physical score (4 items)"
sf36_BP = "Bodily pain (2 items)"
sf36_GH = "General health score (5 items)"
sf36_VT = "Vitality score (4 items)"
sf36_SF = "Social functioning score (2 items)"
sf36_RE = "Role-emotional score (3 items)"
sf36_MH = "Mental health score (5 items)"
;
```

run;

Two summary measures of physical and mental health are constructed from the eight sub-scales, If any item in the calculation is missing, then the summary measure score is missing:

- Physical Health = $(sf36_PF + sf36_RP + sf36_BP + sf36_GH) / 4$
- Mental Health = $(sf36_VT + sf36_SF + sf36_RE + sf36_MH) / 4$

Appendix D - PAT-D Calculation

- Total score = sum all items and divide by 19
- Basic ADLs = sum items 7, 10, 11, 13, 14, 15, & 16 and divide by 7
- Mobility = sum items 2, 3, 5, 6, 18, 19 and divide by 6
- IADLs = sum items 1, 4, 8, 9, 12, 17 and divide by 6

*Items that receive a score of 6 (usually did not do for other reasons) are not included in scoring.

No fewer than 4 items should be used in calculating any subscale score. If fewer than 4 items are available then the score is considered as missing.

Appendix E - Mini Nutritional Assessment - Short Form

The Mini Nutritional Assessment – short Form (SF-MNA®) is a 6-question short form of the Mini Nutritional Assessment (MNA)⁷.

The possible scores for each of the six questions A to F in the CRF are as follows:

Question A: Food intake declined over the past 3 months due to loss of appetite, digestive problem, chewing or swallowing difficulties

- 0 = Severe decrease in food intake
- 1 = Moderate decrease in food intake
- 2 = No decrease in food intake

Question B: Weight loss during the last 3 months

0 = Weight loss greater than 3 kg (6.6 lbs)

- 1 = Does not know
- 2 = Weight loss between 1 and 3 kg (2.2 and 6.6 lbs)
- 3 =No weight loss

Question C: Mobility

- 0 = Bed or chair bound
- 1 = Able to get out of bed/chair, but does not go out
- 2 = Goes out

Question D: Has suffered psychological stress or acute disease in the past 6 months?

- 0 = Yes
- 2 = No

Question E: Neuropsychological problems

- 0 = Severe dementia or depression
- 1 = Mild dementia
- 2 = No psychological problems
- Question F: Body Mass Index (BMI) (weight in kg) / (height in m2) 0 = BMI less than 19 1 = BMI 19 to less than 21 2 = BMI 21 to less than 23 3 = BMI 23 or greater

Total score = sum of scores from all questions. If more than 50% of question responses are missing then the total score is considered as missing.

The total score ranges from 0 to 14, where score 0-7 represents malnourished, 8-11 represents at risk of malnutrition and 12-14 represents normal nutritional status.

The total score is collected in the CRF.

Nutritional Status

- 1 = Normal nutritional status
- 2 = At risk of malnutrition
- 3 = Malnourished

Statistical Analysis Plan Protocol Number: BIO101-CL03

Appendix G - SarQoL Calculation

The SarQoL® questionnaire is composed of 55 items translated into 22 questions rated on a 4-point Likert scale. The questionnaire is scored on 100 points. Higher score reflects a higher quality of life. Items are organized into seven domains: domain 1 'Physical and Mental Health' with 8 items; domain 2 'Locomotion' with 9 items; domain 3 'Body Composition' with 3 items; domain 4 'Functionality' with 14 items; domain 5 'Activities of daily living' with 15 items, domain 6 'Leisure activities' with 2 items, and, at last, domain 7 'Fears' with 4 items. It produces 7 domain scores and 1 overall quality of life score, all between 0 and 100 points.

Appendix F - TSD-OC Calculation

The TSD-OC is composed of 36 items divided into seven sections (pain: 5 items; stiffness: 2 items; activities of daily living (ADL) and indoor mobility: 7 items; housework: 7 items; outdoor activities: 5 items; occupational activities: 4 items and social life: 6 items), which reflect the domains in which individuals experience the most common problems. Individuals are requested to provide a subjective assessment of their disability for each item on a 0–10 visual analogue scale (VAS), where 10 indicates the highest level of disability and 0 indicates no difficulties in performing the task.

The final 'disability scores' is defines as the sum of each item's raw score divided by the maximum possible score, expressed as a percentage according to the following linear transformation: (raw score/max score)*100. For example, a raw score of 90, being 25% of the total possible score (which corresponds to 360), results in a final disability score of 25.

In this way, disability scores can be calculated for each subsections pain, stiffness, ADL and indoor mobility.

Appendix S1 - A SAS macro for Implementing the Bayesian Multiple Imputation Method

Program: impute car only data.sas Purpose: Bayesian MI method for left-censored data Author: Macro Note: multivariate normal data is in wide format including id, varlist values that are < LOD and need imputed are replaced with LOD varlist: variables need imputation, whether MAR or CAR (coarsening at random) covlist: variables that have no missing data are considered as covariates indexlist: binary variables that identify whether the observations of the corresponding variable in the varlist needs imputed this is useful when some values in the varlist are <LOD but do not need to be imputed; otherwise it is just an indicator for data missing or not noimpute: the value that indexlist variables takes if the observations of the variables in the varlist do not need to be imputed lboundlist: impute values > lbound, . represent no bound LODlist: the limit of detection for the normal data, . represents no LOD iteration-# of iterations for Gibbs sampler to converge ndata-# of multiply imputed data sets for each chain nchain-# of independent Markov chain interval-# thinning parameter of the MCMC chain output ndata imputed data sets from each of the nchain chains: can use ndata data sets from nchain different chains or ndata data sets from a single chain (data set called midata org) varlist, indexlist, lboundlist, lodlist need to have the same dimension this program does not track parameter estimates due to memory constraints */ %macro coarsen(data,id,varlist, covarlist,indexlist, noimpute, lboundlist,lodlist,iteration,ndata,nchain,interval, initialseed); proc iml; * read in data; use &data; read all var {&varlist} into zorg; read all var {&id} into pid; %if &covarlist ne %then %do; read all var {&covarlist} into xcov; %end:

read all var {&indexlist} into indexorg; %end; close &data;

Statistical Analysis Plan Protocol Number: BIO101-CL03

%if &indexlist ne %then %do;

Version Final 2.0, Date: 04JUN2021

```
* sample size;
n=nrow(zorg);
call symput('totaln',left(char(n)));
* dimension of multivariate;
p=ncol(zorg);
call symput('dim',left(char(p)));
* dimension of covariates with no missing data;
%if &covarlist ne %then %do;
pcov=ncol(xcov);
%end;
%else %do;
pcov=0;
%end;
* identify LOD for each variable;
%let li=1;
%do %while (%scan(&lodlist, &li, ' ') ne );
%let lod&li= %scan(&lodlist, &li, ' ');
lodorg=lodorg || &&lod&li;
%let li = %eval(&li+1);
%end;
* identify lbound for each variable;
%let lb=1;
%do %while (%scan(&lboundlist, &lb, ' ') ne );
%let lb&lb= %scan(&lboundlist, &lb, ' ');
lborg=lborg||&&lb&lb;
%let lb = %eval(&lb+1);
%end;
* identify the number of observed values for each z;
nobs=j(p,1,0);
* calculate mean and sd of observed data;
mean0=j(p,1,0);
sd0=j(p,1,0);
do k=1 to p;
obs=loc(zorg[,k] >lodorg[k]);
zobs=zorg[,k][obs];
mean0[k]=sum(zobs)/ncol(obs);
sd0[k]=sqrt(1/(ncol(obs)-1)*sum((zobs-mean0[k])##2));
nobs[k]=ncol(obs);
end;
nobs=shape(1:p,p,1)||nobs;
* sort by the number of observed values, descending order;
call sort(nobs, 2, 2);
varorder=nobs[,1];
* rearrange the original data matrix by the number of observed values;
z=j(n,p,0);
lod=j(1,p,0);
lbound=j(1,p,0);
```

Statistical Analysis Plan Protocol Number: BIO101-CL03 Version Final 2.0, Date: 04JUN2021

Page 62 of 69

```
%if &indexlist ne %then %do;
indorder=j(n,p,0);
%end;
do l=1 to p;
z[,1]=zorg[,varorder[1]];
* rearrange lod accordingly;
lod[1]=lodorg[varorder[1]];
* rearrange lbound accordingly;
lbound[1]=lborg[varorder[1]];
* rearrange the indicator for index accordingly;
%if &indexlist ne %then %do;
indorder[,1]=indexorg[,varorder[1]];
%end;
end;
* obtain order information to rearrange to the original variable order
later;
rorder=shape(1:p,p,1)||varorder;
call sort (rorder, 2);
rvarorder=rorder[,1];
* starting number for labeling the imputed data sets;
mi=1;
seed=&initialseed;
* start multiple chains;
%do chain=1 %to &nchain;
* set the nmi to the number of MI for each chain;
%let nmi=&ndata;
* initialize, impute z car and z mar based on observed z;
* null matrix;
z0=
    j(n,p,0);
do i=1 to n;
   do j=1 to p;
   if zorg[i,j]>lodorg[j] then z0[i,j]=zorg[i,j];
   else do;
   z0[i,j]=mean0[j]+ sd0[j] * normal(seed)
                                            ;
   seed=seed+1;
   end;
   end;
end;
* rearrange the initialized data matrix by the number of observed values;
* start Gibbs sampler;
znew=j(n,p,0);
do l=1 to p;
znew[,1]=z0[,varorder[1]];
end;
```

Statistical Analysis Plan Protocol Number: BIO101-CL03 Version Final 2.0, Date: 04JUN2021

Page 63 of 69

```
* save memory space;
store z0;
free z0;
* gibbs sampler for each chain;
%do t=1 %to &iteration;
* for the (t+1) iteration;
* cycle through all p variables;
%do parm=1 %to &dim;
* regression for zj;
* design matrix for zj;
* multivariate in varlist;
%if &dim ne 1 %then %do;
index=setdif(1:p, &parm);
%if &covarlist ne %then %do;
x=j(n,1,1)||znew[,index]||xcov;
%end;
%else %do;
x=j(n,1,1)||znew[,index];
%end;
%end; /* this goes with the dim ne 1 loop */
* univariate in varlist;
%if &dim = 1 %then %do;
%if &covarlist ne %then %do;
x=j(n,1,1) | |xcov;
%end;
%else %do;
x=j(n,1,1);
%end;
%end; /* this goes with the dim = 1 loop */
betahat=solve(x`*x, x`*znew[,&parm]);
residual=znew[,&parm]-x*betahat;
* standard deviation of residual variances;
sighat=sqrt((residual`*residual)/(n-p));
* generate a chi-square random variate;
call streaminit(seed);
chisq=rand('CHISQUARE', n-p);
seed=seed+1;
* a random draw of sig jj from inverse chi-square;
sigtilda=sqrt((n-p))*sighat/sqrt(chisq);
* compute Cholesky decomposition;
chol=root(inv(x`*x));
* generate p+pcov random standard normal variates;
bzdev=j(p+pcov,1,0);
call randseed(seed);
call randgen(bzdev, 'NORMAL', 0, 1);
seed=seed+1;
* a random draw of beta_j from multivariate normal;
betatilda=betahat+sigtilda*t(chol)*bzdev;
```

Statistical Analysis Plan Protocol Number: BIO101-CL03 Version Final 2.0, Date: 04JUN2021

Page 64 of 69

```
* compute mu j;
mu=x*betatilda;
* save memory space;
store x residual;
free x residual;
* identify the observed data, including <LOD but do not need to be
imputed;
* note that z is the rearranged original matrix;
%if &indexlist ne %then %do;
iobs=loc(z[,&parm] >lod[&parm] | indorder[,&parm]=&noimpute);
%end;
%else %do;
iobs=loc(z[,&parm] >lod[&parm]);
%end;
zobs=z[,&parm] [iobs];
* identify the MAR in z j;
imar=loc(z[,&parm] = .);
if ncol(imar) > 0 then do;
mumar=mu[imar];
* impute MAR, greater than lbound if there is one;
if lbound[&parm] ^= . then do;
* generate random uniform variates;
uniform mar=j(ncol(imar),1,0);
call randseed(seed);
call randgen(uniform mar, 'UNIFORM');
seed=seed+1;
lmar=(lbound[&parm]-mumar)/sigtilda;
vmar=CDF('NORMAL', lmar, 0,1) + uniform mar # (1-CDF('NORMAL', lmar,
0,1));
zmar=mumar+sigtilda*probit(vmar);
end; /* this goes with the lbound ne . loop */
* impute MAR, if there is no lbound ;
if lbound[&parm] = . then do;
* generate random standard normal variates;
normal=j(ncol(imar),1,0);
call randseed(seed);
call randgen(normal, 'NORMAL', 0, 1);
seed=seed+1;
zmar=mumar+sigtilda*normal;
end; /* this goes with the lbound = . loop */
end; /* this goes with the imar loop */
* no need to impute CAR;
if ncol(iobs)+ncol(imar)=n then do;
* combine the imputed data and update the design matrix;
z&parm.new=(t(iobs)||zobs) // (t(imar)||zmar);
end;
```

Statistical Analysis Plan Protocol Number: BIO101-CL03 Version Final 2.0, Date: 04JUN2021

Page 65 of 69

```
if ncol(iobs)+ncol(imar) < n then do;
* identify CAR in z j;
%if &indexlist ne %then %do;
icar=loc(z[,&parm] <= lod[&parm] & z[,&parm] ^= . & indorder[,&parm] ^=</pre>
&noimpute);
%end;
%else %do;
icar=loc(z[,&parm] <= lod[&parm] & z[,&parm] ^= .);</pre>
%end;
if ncol(icar) >0 then do;
* generate random uniform variates;
uniform=j(ncol(icar),1,0);
call randseed(seed);
call randgen(uniform, 'UNIFORM');
seed=seed+1;
mucar=mu[icar];
tcar=(lod[&parm]-mucar)/sigtilda;
* impute CAR within the interval lbound and LOD;
if lbound[&parm] ^= . then do;
lcar=(lbound[&parm]-mucar)/sigtilda;
vcar=CDF('NORMAL', lcar, 0,1) + uniform # (CDF('NORMAL', tcar, 0,1) -
CDF('NORMAL', lcar, 0,1));
end; /* this goes with the lbound ne . loop */
* impute CAR < LOD if there is no lbound ;
if lbound[&parm] = . then do;
vcar=uniform # CDF('NORMAL', tcar, 0,1);
end;
* Note that occasionally vcar is close to 1 and cause invalid argument to
probit function;
* print lcar tcar vcar mucar;
test=loc(vcar > 0.9999999);
if ncol(test) > 0 then do;
vcar[test]=0.9999999;
end:
zcar=mucar+sigtilda*probit(vcar);
end; /* this goes with the icar loop */
* combine the imputed data and update the design matrix;
if ncol(imar)>0 & ncol(icar) >0 then do;
z&parm.new=(t(iobs)||zobs) // (t(imar)||zmar) // (t(icar)||zcar);
end;
else if ncol(imar)=0 & ncol(icar) >0 then do;
z&parm.new=(t(iobs)||zobs) // (t(icar)||zcar);
end;
else if ncol(imar)>0 & ncol(icar) =0 then do;
z&parm.new=(t(iobs)||zobs) // (t(imar)||zmar);
end;
```

Statistical Analysis Plan Protocol Number: BIO101-CL03 Version Final 2.0, Date: 04JUN2021

Page 66 of 69

```
end; /* this goes with the < n loop */
* sort the imputed data by id;
call sort(z&parm.new,1);
* remove id;
z&parm.mi=z&parm.new[,2];
* update the data matrix;
* repalce z j from iteration t with z_j from iteration (t+1);
%if &dim ne 1 %then %do;
zcom= znew[,index]||z&parm.mi;
* organize the order of the columns from z1 to zp;
order=index|| &parm ;
%end; /* this goes with the dim ne 1 loop */
%if &dim = 1 %then %do;
zcom= z&parm.mi;
order= &parm ;
%end; /* this goes with the dim = 1 loop */
zcom=t(order//zcom);
call sort (zcom, 1);
znew=t(zcom[,2:n+1]);
* save memory space;
store mu z&parm.new z&parm.mi zcom;
free mu z&parm.new z&parm.mi zcom;
%end; /* this goes with the parm loop */
* output the m data sets after the convergence for specified intervals
apart;
%if (&t=%eval(&iteration-&interval * (&nmi-1)) ) %then %do;
impute=j(n,1,&chain)||j(n,1,mi)||pid||znew;
* rearrange to the original variable order;
impute org=j(nrow(impute),p+3,0);
do m=1 to p;
impute org[,m+3]=impute[,rvarorder[m]+3];
end;
impute org=impute[,1:3]||impute org[,4:p+3];
midata org=midata org//impute org;
mi=mi+1;
%let nmi=%eval(&nmi-1);
* save memory space;
store impute impute org;
free impute impute_org;
%end; /* this goes with the output loop */
```

Statistical Analysis Plan Protocol Number: BIO101-CL03 Version Final 2.0, Date: 04JUN2021

```
%end; /* this goes with the iteration loop */
%end; /* this goes with the nchain loop */
* get variable names for output dataset;
vlist="&varlist";
 %do vi=1 %to &dim;
vname&vi='mi_'+scan(vlist, &vi);
call symputx("varname&vi", vname&vi);
%end;
* note that all variables in the output dataset contained imputation of
missing and left-censored data;
create midata_org from midata_org
[colname={'chain' '_imputation_' "&id"
%do vi=1 %to &dim;
"&&varname&vi"
%end;
 }];
append from midata_org;
quit;
%mend;
* %coarsen(data=walk,
           id=pidn,
           varlist=speed m3 speed m69 speed lod m3 speed lod m69,
           indexlist=complete m3 complete m69 complete m3 complete m69
           noimpute=1,
           covarlist=speed m0,
           lboundlist=0 0 0 0,
           lodlist=. . 0.44 0.44,
           iteration=2000,
           ndata=5,
           nchain=5,
           interval=100.
            initialseed=155504946);
```

Statistical Analysis Plan Protocol Number: BIO101-CL03

